8.2.3. Neutralizing Antibodies to FIX

FIX inhibitor level reflects the immunogenicity response to FIX. It is collected over time during the study. The level of FIX inhibitor will be summarized by treatment cohort and by visit for baseline, post-baseline and change from baseline values. Corresponding listing will be provided. The mean and standard error by cohort will be plotted by timepoint and treatment cohort.

8.2.4. Presence and shedding of AAV2/6 vector DNA

Presence and shedding of AAV2/6 vector DNA, by PCR in plasma, saliva, urine, stool and semen over time is conducted in lab section over time till week 52. The level of vector genome from each type of sample will be summarized by visit. Corresponding listing will be provided. The mean and standard error by cohort will be plotted for AAV shedding in blood and in serum by timepoint and treatment cohort.

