#### **6.7 Weeks 2, 4, 6, 8, 10, and 12 (+/- 3 day)**

The following evaluations will be performed at each visit unless stated otherwise:

1. AE assessment
2. Assessment of concomitant medications
3. Physical exam
4. Weight
5. Vital signs
6. Abdominal exam for hepatomegaly
7. Neurologic cranial nerve exam and muscle strength testing of the upper extremities including shoulder, elbow and hands (Week 12 only)
8. Chemistry, liver and metabolic panel (liver panel will be performed 2 times a week. Local lab may be used for liver panel if clinically indicated and following consultation with the Medical Monitor)
9. CBC with differential and platelet count (Weeks 4, 8, and 12)

10. Coagulation screen: PT, INR, and PTT (Weeks 4, 8, and 12)
11. FIX antigen (Weeks 4, 8, and 12)
12. FIX activity level (will be measured once a week)
13. FIX inhibitor level (Weeks 4, 8, and 12)
14. Total antibodies to AAV2/6 (Weeks 4, 8, and 12; exploratory test)
15. ZFN immunogenicity (weeks 4, 8, and 12; exploratory test)
16. PCR of vector genomes in plasma, saliva, urine, stool, and semen (Weeks 2, 4, 8 and 12 only)
17. Assessment of bleeding episodes and FIX concentrates usage
18. Liver MRI or equivalent imaging technology (Week 12 only)
19. Circulating alpha fetoprotein level (Week 12 only)
20. ACTH stimulation test (only performed if at the end of prednisone or equivalent taper)
21. Administration of prednisone (or equivalent) if indicated (see [Appendix 3](#))

Any subject who has an elevated alpha fetoprotein and MRI mass suspicious (or equivalent) for hepatocellular carcinoma (HCC) or greater than 2 cm will undergo biopsy using surgical doses of Factor IX replacement. Histopathologic examination and genomic analysis (e.g., sequencing of the albumin locus and integration site analysis) will be performed to determine the origin and nature of the tumor. Detailed instruction on sample collection and tissue preparation for genomic analysis is provided in the [Appendix 2](#).

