## **6.8 Weeks 16, 20, 24, 28, 32, 36, 40, 44, 48, and 52 (+/- 1 week)**

The following assessments are performed at each visit unless stated otherwise.

1. AE assessment
2. Assessment of concomitant medications
3. Physical exam
4. Weight
5. Vital signs
6. Abdominal exam for hepatomegaly
7. Neurologic cranial nerve exam and muscle strength testing of the upper extremities including shoulder, elbow and hands (Weeks 24 and 52 only)
8. Chemistry, liver, and metabolic panel (Liver panel will be performed twice a week until termination of steroid treatment if on steroid treatment. Local lab may be used for liver panel if clinically indicated and following consultation with the Medical Monitor).
9. CBC with differential and platelet count (Weeks 28 and 52 only)

10. Coagulation screen (PT, INR, and PTT)
11. FIX antigen and activity level (FIX activity will be measured weekly if subject is receiving steroid treatment).
12. FIX inhibitor level
13. Total antibodies to AAV 2/6 (Weeks 24, 36, and 52 only; exploratory test)
14. ZFN immunogenicity (Weeks 24, 36, and 52 only; exploratory test)
15. PCR of vector genomes in plasma, saliva, urine, stool, and semen (unless two previous consecutive specimens have been negative)
16. Assessment of bleeding episodes and FIX concentrates usage
17. Liver MRI or equivalent imaging technology (Weeks 24 and 52 only)
18. Circulating alpha fetoprotein level (Weeks 24 and 52)
19. Administration of prednisone (or equivalent) if indicated (see [Appendix 3](#))
20. ACTH stimulation test (only performed if at the end of prednisone [or equivalent] taper)

Any subject who has an elevated alpha fetoprotein and MRI mass suspicious for hepatocellular carcinoma (HCC) or greater than 2 cm will undergo biopsy using surgical doses of Factor IX replacement. Histopathologic examination and genomic analysis (e.g., sequencing of the albumin locus and integration site analysis) will be performed to determine the origin and nature of the tumor. Detailed instruction on sample collection and tissue preparation for genomic analysis is provided in the [Appendix 2](#).

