### **6.10 Early Termination Visit (ETV)**

Subjects who discontinue from the study prematurely or are withdrawn from the study will be asked to return to the study site for an Early Termination Visit (ETV). It is at the discretion of the Investigator to waive any procedures if it has been performed within the standard interval of scheduled study visits per protocol.

The following assessments and procedures will be performed at the ETV:

1. AE assessment
2. Assessment of concomitant medications
3. Physical exam
4. Weight
5. Vital signs
6. Abdominal exam for hepatomegaly
7. Neurologic cranial nerve exam and muscle strength testing of the upper extremities including shoulder, elbow and hands
8. Urinalysis with microscopic exam
9. Chemistry, liver, and metabolic panel
10. CBC with differential and platelet count
11. Coagulation screen (PT, INR, and PTT)
12. FIX antigen and activity levels
13. FIX inhibitor level
14. Assessment of bleeding episodes and FIX concentrates usage
15. ACTH stimulation test (only performed if at the end of prednisone [or equivalent] taper)
16. Liver MRI or equivalent imaging technology (if not performed within 6 months prior to the ETV)
17. Circulating alpha fetoprotein level
18. Vector genome in plasma, saliva, urine, stool, and semen by PCR

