APPENDIX 1. SCHEDULE OF EVENTS									
Procedure	Screening	Baseline (w/in 21 days before SB-FIX infusion)	Hospitalization or Acute Care Facility		Day 7 (+/-1 day)	Weeks 2, 4, 6, 8, 10, 12 (+/- 3 day)	Weeks 16, 20, 24, 28, 32, 36, 40, 44, 48, 52 (+/- 1 wk)	Months 15, 18, 21, 24, 27, 30, 33, 36/EOS* (+/- 1 M)	Early Termination Visit
			Day 0	Day 1					
Exploratory samples (h)		X							
Liver Biopsy (i)								X (EOS only)	

\* Study subjects may participate in the LTFU Study after 12 months of follow-up in the SB-FIX-1501 study, in which case an EOS visit may be conducted any time after Week 52 in combination with or before the next scheduled study visit.

- a. Height will be measured at Screening Visit only.
- b. At Screening, liver panel will be performed two times at least one week apart. Liver panel will be tested twice per week for the first 12 weeks after the SB-FIX infusion. LFT for the baseline visit must be performed within 1 week of infusion.
- c. Subjects will use a diary to record bleeding episodes, factor infusions, and concomitant medications starting at their baseline visit through their last visit.
- d. ACTH stimulation test will be performed at Baseline for all subjects, and the test will be performed again only at the end of steroid taper. ACTH test will be performed at the early termination visit if subject is on a steroid regimen at the time of their visit.
- e. Vector genomes in plasma, saliva, urine, stool, and semen by PCR (unless two previous consecutive specimens have been negative). On Day 1, the only vector genome analysis performed is in plasma (12 hours after infusion).
- f. Only for subjects with no FIX sequencing previously
- g. Any subject who has an elevated alpha fetoprotein and MRI mass suspicious for hepatocellular carcinoma (HCC) or greater than 2 cm will undergo biopsy using surgical doses of Factor IX replacement. A MRI of the liver can be replaced by an abdomen CT-scan (or any equivalent imaging technology) – with vascular phases specific for a search of a liver mass – in case the subject has a contraindication to MRI (for example history of hip replacement).
- h. Blood samples for sEGFR and Gal3BP will be collected and stored for future analysis.
- i. At the end of EOS visit, subjects may be asked to provide a liver biopsy, at the discretion of the Principal Investigator and Sangamo Medical Monitor.

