3.4. Dose Modifications

No dose modifications are possible within an individual subject as this is a single infusion study.

4. General Statistical Considerations

Study day will be calculated as event/assessment date - date of SB-FIX infusion. Thus, the date of SB-FIX infusion is considered as Day 0. The relative study day for assessment will be derived as the assessment date subtracted from the date at Day 0.

Baseline is defined as the last non-missing assessment prior to the SB-FIX infusion. Measurements that are obtained after infusion will be considered as post-baseline values. Change from baseline is defined as post-baseline assessment minus baseline assessment.

Summary tables will be provided when there is more than one enrolled subject in a cohort. Otherwise, data will be presented in the form of a listing.

Continuous variables will be summarized using the following descriptive statistics: the number of subjects (n), mean, standard deviation (SD), median, minimum and maximum,

where appropriate. Categorical variables will be summarized using the frequency count (n) and percentage (%) of subjects for each category, where appropriate.

No imputation will be performed for missing data unless otherwise specified.

Data will be displayed in all listings sorted by treatment cohort and subject identifier.

All analyses will be conducted using SAS[®] Version 9.3 or higher. The Medical Dictionary for Regulatory Activities (MedDRA) version 23.0 will be used for coding adverse events. Prior or concomitant medication data will be coded using the World Health Organization (WHO) Drug Dictionary Global B3 March 2020.

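### Vector-shedding means by visit leave out subjects whose PCR stopped after two negatives, so a late cohort mean is too high whenever a subject still tested is positive (minor, descriptive)

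*SAP*

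**What the plan says.** **Sampling.** Protocol 6.8 schedules vector PCR in plasma, saliva, urine, stool and semen at Weeks 16 to 52 "unless two previous consecutive specimens have been negative". Footnote e of the Schedule of Events (Appendix 1) attaches the same condition to the whole PCR row, with no visit limit. Protocol 6.7 gives Weeks 2, 4, 8 and 12 without it. The rule thus applies from Week 16 at the latest. An individual stop may come later, or never. Protocol 6.10 lists a further PCR sample at the Early Termination Visit and does not repeat the condition there.

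**Analysis.** SAP 8.2.4 states: "The level of vector genome from each type of sample will be summarized by visit". It adds: "The mean and standard error by cohort will be plotted for AAV shedding in blood and in serum". That plot is the only place in 8.2.4 where a mean is named, and its sample types do not match the protocol's five. For the table, a mean comes in through the default statistics for continuous variables in SAP section 4, which apply where appropriate.

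**Missing values.** SAP section 4: "No imputation will be performed for missing data unless otherwise specified". SAP 8.2.4 specifies no exception. It does not mention the stopping rule, and it does not say what value a negative result takes.

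**The concern.** Most missing values are missing for reasons that may or may not relate to the outcome. Here the protocol creates the gap, and the trigger is the outcome itself: a subject drops out of the average by testing negative twice. The subjects left at a late visit are those not yet twice negative. Their mean describes that remainder, but it would be printed and plotted as the cohort's level at that visit.

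The cohorts are very small. Each is planned with two adults and may grow to four (Protocol 3.3 and 10.2). One stop in a cohort of two turns the plotted mean into a single subject's value, for which no standard error exists. The small-number safeguard in SAP section 4, "Summary tables will be provided when there is more than one enrolled subject in a cohort", counts enrolled rather than sampled subjects and concerns tables, so it does not reach the plot.

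What is at stake is the description of a secondary endpoint. A dose cohort could appear to clear vector more slowly than it did.

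**Working it through.** The plan gives no shedding figure to reproduce, so the check is algebra, an example and an illustration.

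**Formula.** Let N be the subjects in the cohort, n those still sampled, S the sum of the sampled values, and L the value given to a negative. Assume stopped subjects stay negative, and read the stopping rule separately for each sample type.

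- Observed mean = S/n
- Cohort mean = (S + (N − n)L)/N
- Ratio = N·S / [n(S + (N − n)L)]

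If L = 0 and S > 0, the ratio is N/n. If L > 0, it is smaller, but still above 1 whenever n < N and some sampled value exceeds L. It is 1 if nobody has stopped or if everyone still tested is negative.

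**Upper bounds (L = 0).**

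- N = 2, n = 1: 2/1 = 2
- N = 4, n = 3, 2, 1: 4/3 = 1.33, 4/2 = 2, 4/1 = 4

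**Dependence on L.** Take N = 4 with one subject left at 100. L = 0 gives 100/25 = 4.0. L = 10 gives 100/32.5 = 3.1. L = 50 gives 100/62.5 = 1.6.

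**Example with assumed values.** Cohort of two, detection limit 100. Subject A is negative at Weeks 8 and 12 and stops. Subject B follows 10^(5 − 3w/24), where w is the week.

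| Week | B | Plotted mean | Both subjects, L = 0 | Ratio | Both subjects, L = 100 | Ratio |
|---|---|---|---|---|---|---|
| 16 | 1000 | 1000 (no SE) | 500 | 2.00 | 550 | 1.82 |
| 20 | 316 | 316 (no SE) | 158 | 2.00 | 208 | 1.52 |

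At Week 12 both are sampled and B is 3162. The mean is 1581 with L = 0 and 1631 with L = 100. From Week 12 to Week 16 the plotted mean falls 1581/1000 = 1.6-fold, against 1581/500 = 3.2-fold for both subjects (L = 0). With L = 100 the falls are 1631/1000 = 1.6-fold and 1631/550 = 3.0-fold. Median and minimum come from the same reduced sample: at Week 16 both are 1000, against 500 and 0 for the two subjects with L = 0.

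**How often? An illustration only.** None of these inputs comes from the documents except the visit schedule and the rule. Assumptions: log-linear fall from 10^5 to 10^2, log-normal clearance time with log-scale SD 0.7, rule applied from Week 16, N = 2, and 20,000 simulated cohorts per setting. For median clearance of 24, 16, 12 and 8 weeks:

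- some visit up to Week 52 has an overstated mean: 62, 50, 39 and 22% of cohorts
- some visit has only one subject sampled: 89, 88, 82 and 69%
- Week 24 is overstated: 28, 28, 21 and 10%

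Varying the SD from 0.4 to 1.0 widens the first range to 5–66% and the second to 62–89%. With negatives set at the limit and SD 0.7, the median ratio at affected visits is 1.63 to 1.79, and 26 to 39% of those visits are below 1.5.

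**The case against.** The strongest reply is that little depends on this mean. SAP section 1 rules out hypothesis testing. No escalation or stopping rule in the documents uses a shedding mean, and the sperm-donation condition in Protocol 4.1 rests on each subject's own semen samples. With two subjects per cohort, the table's n and the subject listing show who has stopped. All of this stands, and it is why the point is minor. It does not correct the plot, for which SAP 8.2.4 does not require n.

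Second, an observed-case summary with its n is a legitimate description of the subjects tested, and treating untested subjects as negative is itself an assumption. That also stands. It argues for individual profiles first and a carried-negative proportion only as a labelled supplement.

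Third, the table mean is not firmly prescribed, because the default statistics apply where appropriate. This is true, but the plotted mean is explicit.

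A reader might go further and infer that late means are always doubled, or that the curve will rise while shedding falls. The documents do not support either. The factor of 2 is a bound that depends on coding negatives as 0, which the SAP does not state. A rise is possible, but in the SD 0.7 illustration it occurred at only 40, 20, 10 and 3% of the visits where one subject had just stopped and another was still sampled.

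**Conclusion.** The point holds, as a minor one. Following the protocol's stopping rule and SAP 8.2.4 as written, the late-visit mean is biased upward at any visit where at least one subject has stopped and stayed negative and a subject still tested is positive. The factor is at most N/n, so 2 for two subjects with one left and 4 for four with one left, and it is smaller if negatives take a value above 0. With one subject sampled, the plotted standard error does not exist.

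The direction rests on two assumptions: stopped subjects remain negative, which is the premise of stopping, and negatives are coded below the positive values still measured. The size depends on a detection limit and coding rule that the documents do not give, and the frequency on decay patterns they do not give either.

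A reader might infer a threat to subject safety or to dose decisions. The documents do not support that, since nothing in them acts on this mean.

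**What to change.** In SAP 8.2.4:

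1. Replace the mean and standard error plot with individual subject profiles for each sample type, negatives drawn at the detection limit and the stop marked. Name the sample types in the protocol's terms. If a mean is kept, show n sampled, give no mean or standard error where fewer than two subjects are sampled, and state the value used for a negative.
2. By visit, sample type and cohort, report number positive, number tested and number stopped under the two-negative rule. As a labelled supplement, give number positive over Safety-set subjects still in follow-up, with stopped subjects counted as negative and any later actual result (such as the Early Termination sample) overriding. State this denominator, because the default in SAP 4.2.2 is the whole Safety set.
3. List, per subject and sample type, the time to the first of two consecutive post-infusion negatives.

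The cost is SAP text and a little programming, with no new samples and no change to conduct. The downside lies in the supplementary proportion: if vector reappeared in an untested subject, positivity would be understated by 1/2 = 50 percentage points per missed subject in a cohort of two and 1/4 = 25 in a cohort of four. The tested and stopped counts beside it keep that visible, and the individual profiles carry no such assumption.

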8.2.5. Vital Signs

The vital sign data collected after infusion until 2 hours post-infusion will be pooled for each subject and the mean of pooled data will be summarized by cohort as one timepoint,

ie 2 hour post-infusion timepoint. The data collected at Baseline, and post-infusion will be summarized by timepoint for each cohort. Change from baseline will be summarized too. The vital sign data will be listed.

9. Other Analysis

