#### **6.4 Day 0 SB-FIX Infusion**

Subjects will be hospitalized or admitted to an acute care facility for SB-FIX infusion and will remain in the hospital or acute care facility for 24 hours after the end of the infusion for observation, and will be discharged when all AEs, concomitant medications, and all vital signs (temperature, pulse, respiratory rate, and blood pressure) are stable.

The following evaluations will be performed prior to SB-FIX infusion:

1. AE assessment
2. Physical exam
3. Weight
4. Assessment of concomitant medication
5. Vital signs: temperature, pulse respiratory rate, and blood pressure within 15 (+/- 5) minutes of the start of the infusion, every 15 (+/- 5) minutes until stable, then 30 (+/- 5) minutes until 2 hours post-infusions, then every hour (+/- 10 min) for 3 hours, then every 2 (+/-10 min) hours for 4 hours and then every 4 (+/- 15 min) hours until discharge.
6. Chemistry, liver, and metabolic panel
7. CBC with differential and platelet count
8. Coagulation screen (PT, INR, and PTT)
9. Assessment of bleeding episodes and FIX concentrates usage
10. Administration of prednisone (or equivalent) if indicated (see [Appendix 3](#))

SB-FIX will be infused via a peripheral vein catheter over a period of 2-8 hours depending on subject's cohort assignment and body weight.

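### SAP 8.2.5 reduces each subject's vital signs up to 2 hours post-infusion to one mean, which dilutes a transient infusion reaction in the table, and leaves the window's anchor (start or end of infusion) undefined

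*SAP*

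**What the plan says.** SAP 8.2.5 defines the data to be pooled as "The vital sign data collected after infusion until 2 hours post-infusion". These readings "will be pooled for each subject and the mean of pooled data will be summarized by cohort as one timepoint", and the SAP names the result the "ie 2 hour post-infusion timepoint". It continues: "The data collected at Baseline, and post-infusion will be summarized by timepoint for each cohort". Change from baseline is also summarized and the vital-sign data are listed. No within-subject minimum, maximum or largest change is planned.

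The statistics come from SAP Section 4: "the number of subjects (n), mean, standard deviation (SD), median, minimum and maximum", where appropriate. The same section takes the last assessment before infusion as baseline and adds: "Measurements that are obtained after infusion will be considered as post-baseline values". Readings during infusion are not mentioned.

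Protocol 6.4 starts the readings around the start of the infusion and continues them "every 15 (+/- 5) minutes until stable, then 30 (+/- 5) minutes until 2 hours post-infusions", "then every hour (+/- 10 min) for 3 hours", and then at wider intervals until discharge. It gives the infusion length as 2 to 8 hours. Protocol 7.1.2 requires vital signs to be monitored while the product is being infused.

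**The concern.** The primary objective is safety and tolerability. Protocol 7.1.2 names transient fever among the possible side effects of infusion, and 7.1.3 foresees anaphylaxis and severe hypotension. These are short events, and a mean over a window is poorly suited to showing them. The period sampled most often on the infusion day is reduced to one number, whereas later, sparser readings keep their own timepoints. The label adds to the problem, because a reader will take it for the reading at 2 hours.

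The anchor is a second, smaller matter. The SAP does not say whether the window and the post-baseline period begin when the infusion starts or when it ends. Two programmers could build different tables from the same data. Under one of the two readings, values recorded during infusion are neither baseline nor post-baseline and appear in no stated summary.

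The SAP already uses extremes where they matter: in 8.1.2 the liver panel shift table takes the extreme post-baseline category.

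**Working it through.** The plan gives no figure to reproduce here. The check is simple dilution arithmetic.

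**Inputs from the documents.** The 30-minute interval up to 2 hours post-infusion and the infusion length of 2 to 8 hours are from Protocol 6.4. The two adults initially planned per dose cohort are from SAP 3.1.

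**Assumptions, not from the documents.** Baseline systolic pressure is 120 mmHg. One reading is 75 mmHg (a fall of 45), the rest are at baseline, and the other subject in the cohort is unchanged.

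**Formulas.** Readings pooled: n = window length in hours x 2. Change shown for the subject = -45 x k/n, where k is the number of low readings. Change shown for a cohort of 2 = half of that.

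| Window | n | Subject, k = 1 | Cohort of 2 |
|---|---|---|---|
| End of infusion to +2 h | 2 x 2 = 4 | -45/4 = -11.3 | -5.6 |
| Start of a 2 h infusion to +2 h | 4 x 2 = 8 | -45/8 = -5.6 | -2.8 |
| Start of an 8 h infusion to +2 h | 10 x 2 = 20 | -45/20 = -2.3 | -1.1 |

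**Effect on minimum and maximum.** With the end anchor the subject's tabulated value is 120 - 11.25 = 108.75 mmHg. The cohort minimum is therefore 108.75, although a reading of 75 was recorded. In the same way, one temperature of 39.0 C among readings of 37.0 C gives 37.0 + 2.0/4 = 37.5 C as the cohort maximum.

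**A longer event.** With 2 of 4 readings low, the mean shows -45 x 2/4 = -22.5 mmHg. A sustained change therefore remains visible.

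**Readings left out under the end anchor.** At 30-minute intervals an infusion of 2 to 8 hours yields 2 x 2 = 4 to 8 x 2 = 16 readings per subject with no stated summary.

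**Detail kept before and after 2 hours.** Under Protocol 6.4 the later readings to 24 hours after the end number 3 hourly + 2 two-hourly + 3 four-hourly = 8, each with its own timepoint. The 4 earlier ones, 4/12 = 33% of the total, share one.

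**With the fix.** A per-subject largest change shows -45 mmHg whichever anchor is used, provided that the reading falls in a defined window.

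**The case against.** The strongest reply is that nothing is lost from the data. Individual readings are listed by cohort and subject, and with at most 16 subjects a reader can go through them. A sign that worsens from baseline can be an adverse event under Protocol 9.1.1, and SAP 8.1.1 tabulates such events by grade. The primary endpoint names adverse events and laboratory changes, not vital signs. Analyses for the safety committee are in a separate document. All of this stands, and it limits the harm, but the table remains uninformative about the events it should show. The adverse-event route depends on investigator reporting, since the grade-based reporting rule in Protocol 9.3 covers laboratory results only.

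Pooling also has a reason. Readings every 15 minutes until stable give subjects different reading times, so common nominal times before 2 hours are hard to define. That explains why separate timepoints were avoided, but it does not favor a mean over an extreme.

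The 15-minute rule also limits how much dilution can be claimed. One might count 8 readings after the end, or 40 from the start of an 8-hour infusion, and set one abnormal value among them. Those counts need 15-minute readings throughout, which Protocol 6.4 provides only until the subject is stable. An unstable subject is sampled more often while unstable, so the mean leans towards the event. For example, four low readings in the first hour and two normal ones in the second show -45 x 4/6 = -30 mmHg.

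Finally, extremes depend on the number of readings. For independent normal readings with no drug effect, the expected minimum is about -1.03 SD with 4 readings and -2.07 SD with 32 (an 8-hour infusion at 15 minutes throughout). Because infusion length depends on cohort and weight, infusion-period extremes could suggest a cohort difference that is not real. This is a fair caution and is taken up in the fix.

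**Conclusion.** The point holds, with modest impact. The single mean dilutes a transient reaction in the only vital-sign table planned for the window, and the tabulated extremes are extremes of subject means. With an end anchor and 30-minute readings, one reading 45 mmHg low shows as about -11 mmHg for the subject and -6 mmHg in a cohort of 2. With a start anchor the subject's change shows as about -6 to -2 mmHg. The size of the fall is assumed. The intervals and infusion lengths are the protocol's.

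Three stronger readings are not supported:

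- A reader might infer that the window has no start. The SAP does give one, after infusion, and fails only to say start or end. Protocol usage leans towards the end: 6.4 counts the 24-hour observation from the end of infusion, and 6.5 describes the same period as after the infusion. One usage points the other way: the plasma sample that 6.5 times at 12 hours from initiation is 12 hours after infusion in Appendix 1, note e.
- A reader might infer that a reaction would vanish or always look near baseline. With an end anchor one of four readings still carries 25% of its change, a sustained fall stays visible, and the listing and adverse-event tables remain.
- A reader might add that Protocol 7.1.3 describes vital-sign timing differently from 6.4. It does, but the SAP pools whatever was collected, so the point does not depend on it.

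No planned decision depends on this table.

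**What to change.** - In SAP 8.2.5 and SAP Section 4, state whether after infusion is measured from the recorded start or end of the infusion, and assign readings taken during infusion to a named period.
- Keep the mean if wanted, but label it a window mean, not a 2-hour timepoint.
- Add each subject's minimum, maximum and largest change from baseline for the fixed 0-2 hour window after the end of infusion and, separately, for the infusion period. Show the number of readings beside each.
- Use the fixed 0-2 hour window as the main comparison. Read infusion-period extremes with their reading count and do not compare them directly between cohorts, because they depend on infusion length and sampling.

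The cost is a few sentences in the SAP and a few more table rows, from data that the protocol already collects.
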